## 4. Identifying high-risk cases

In the past years we have developed several assays, which might enhance the clinical prediction. In the present project this will be possible for the first time. We will evaluate the added diagnostic value of the following assays:

- Platelet respiratory burst assay. The interaction of opsonized platelets with phagocytic cells using the respiratory burst as read out.
- Fucosylation level of anti-HPA1a antibody.
- Interaction of anti-HPA-1a with FcRIIIa. The interaction of the antibodies with the FcRIIIa is highly dependent on the fucosylation level of the antibody. Directly measuring this interaction would be a relative simple approach to measure the level of fucosylation as well as the avidity of the antibody.
- Effect on the integrity of endothelial layer.
- Effect on platelet aggregation. Alloantibodies against GPIIIa can interfere with its function. The inhibition of platelet aggregation will be measured over time.
- C-reactive protein (CRP) concentration in the maternal plasma. Since we found that CRP enhances antibody induced phagocytosis, and CRP levels are slightly elevated in some FNAIT cases, maternal CRP levels will be determined.

### 8.4 Withdrawal and replacement of individual subjects

Subjects can leave the study at any time for any reason. After withdrawal individual subjects will not be replaced.

### 8.5 Follow-up of subjects withdrawn from treatment

*Not applicable*

### 8.6 Premature termination of the study

There are no predefined criteria for terminating the study prematurely.

## **9 SAFETY REPORTING**

### **9.1 Section 10 WMO event**

In accordance to section 10, subsection 1, of the the Medical Research Involving Human Subjects Act (in Dutch: Wet Medisch-wetenschappelijk Onderzoek met Mensen; WMO), the investigator will inform the subjects and the reviewing accredited Medical research ethics committee (in Dutch: medisch ethische toetsing commissie; METC) if anything occurs, on the basis of which it appears that the disadvantages of participation may be significantly greater than was foreseen in the research proposal. The study will be suspended pending further review by the accredited METC, except insofar as suspension would jeopardise the subjects' health. The investigator will take care that all subjects are kept informed.

### **9.2 AEs, SAEs and SUSARs**

*Not applicable*

### **9.3 Annual safety report**

*Not applicable*

### **9.4 Follow-up of adverse events**

*Not applicable*

### **9.5 Data Safety Monitoring Board / Safety Committee**

*Not applicable*

## 10 STATISTICAL ANALYSIS

### 10.1 Primary study parameter(s)

- HPA-1a alloantibodies           categoric variable       quantitative
- Clinically relevant FNAIT       categoric variable       quantitative
  - Perinatal death
  - ICH
  - Internal organ haemorrhage other than ICH

### 10.2 Secondary study parameter(s) and other study parameter(s)

*Categorical data:*

- Neonatal bleeding signs
- Neonatal treatment of thrombocytopenia
- Neonatal morbidity: need for other treatments, congenital abnormalities, causes of increased bleeding tendency
- Demographic: ethnicity
- Pregnancy related
- Delivery related: Apgar scores, mode and place of delivery, fetal distress, sex
- Obstetric and medical history

*Continuous variables:*

- Laboratory findings neonate: platelet count, haemoglobin level, CRP
- Neonatal morbidity: days in hospital
- Maternal characteristics: age
- Delivery related: GA at birth, birth weight
- Medical history: BMI

*Further specification of variables can be found in chapter 8.1.*

#### *Statistical analysis*

For comparison of the secondary study parameters to a control group we will be using the HPA-1a negative women without the formation of alloantibodies as well as HPA-1a positive cases. For categorical variables we will be using Pearson’s chi-square tests and Fisher’s exact tests when applicable and for continuous variables we will be using Student’s t-test or Mann-Whitney test, as appropriate.

We expect perinatal death or ICH due to FNAIT to be the most infrequent outcome. As described before we expect a total of 10 cases of ICH in our study population. In the controls we expect 0-1 ICH will develop. This will lead to a significant difference between the study group and the controls (P<0.0001).

	Case (As+)	Control (As-)	
ICH +	10 (a)	1 (c)	11
ICH-	110 (b)	359 (d)	469
	120	360	480

*Relative risk:  $a/(a+b)/c/(c+d) = (10/120)/(1/360) = 0,0833/0,00278=30$*

*Fisher exact test:  $p < 0.0001$*

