#### 8.1.3 Other study parameters

- Baseline characteristics
  - Demographic: age, ethnicity
  - Medical history: idiopathic thrombocytopenic purpura, bloodtype (ABO and RhD and Rhc), body-mass index
  - Obstetric history: live births, spontaneous abortions, intrauterine fetal demise, mode and GA of previous deliveries.
  - Pregnancy related: gravidity, parity, pre-eclampsia, gestational diabetes, medication, smoking, obstetric care giver
  - Delivery related: GA at birth, mode of delivery, Apgar Scores, perinatal asphyxia/fetal distress, birth weight, male/female sex, place of delivery (home, hospital primary care practice, hospital secondary care practice, tertiary hospital)

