### 8.2 Randomisation, blinding and treatment allocation

For every HPA-1a negative sample, the independent technicians performing the serological HPA-1a typing will select the three consecutive HPA-1a positive samples with an adequate amount of sample available. Those will be included as positive controls and material will be stored next to the HPA-1a negative samples as well. The researchers, when collecting clinical informative, will be blinded for the results of the serological HPA-1a typing as well as the HPA-1a alloantibody detection.

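### Section 10.2 fixes only unadjusted tests for comparing antibody-positive women with unmatched controls, although parity, age and ethnicity are collected and may plausibly differ between the groups

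*Protocol*

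**What the plan says.** The comparison is set out under Statistical analysis in Protocol section 10.2. On the first control group: "For comparison of the secondary study parameters to a control group we will be using the HPA-1a negative women without the formation of alloantibodies". The same sentence names HPA-1a positive women as a second control group. On tests for categorical outcomes: "For categorical variables we will be using Pearson’s chi-square tests and Fisher’s exact tests when applicable". Neither of these takes a covariate. The rule for the remaining outcomes is of the same kind: "for continuous variables we will be using Student’s t-test or Mann-Whitney test, as appropriate". The protocol mentions no regression, stratification or matching.

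Section 8.2 describes how HPA-1a positive controls are found: for each HPA-1a negative sample the technicians "will select the three consecutive HPA-1a positive samples with an adequate amount of sample available". Section 3 calls these controls random. Neither section matches them on any maternal characteristic.

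Section 8.1.3 shows that the obvious covariates are recorded: "Demographic: age, ethnicity" and "Pregnancy related: gravidity, parity, pre-eclampsia, gestational diabetes, medication, smoking, obstetric care giver". Section 10.2 carries ethnicity, maternal age and the pregnancy-related variables into its list of variables, but no named test uses them as covariates.

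**The concern.** This is a non-randomised comparison, so the groups can differ in more than antibody status. Two differences are plausible from the protocol's own account.

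- **Ethnicity.** The Summary and section 1 give the 2.1% HPA-1a negative rate for Caucasians. HPA-1a negative women may therefore have a different ethnic mix from unmatched HPA-1a positive women.
- **Parity.** Section 1 attributes antibody formation to incompatibility between mother and fetus. If fetal exposure causes immunisation, women with more earlier pregnancies have had more opportunity for it, so antibody-positive women may be more often parous than antibody-negative women.

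Either factor may also be related to hospital days, neonatal morbidity, birth weight and gestational age at birth. A crude difference in these outcomes could then be read as an effect of FNAIT when part of it reflects who the mothers are, or it could hide part of a real effect. The tests named in section 10.2 cannot separate the two.

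**Working it through.** **1. The plan's own figure.** Section 10.2 illustrates the ICH comparison with 10/120 antibody-positive and 1/360 control.

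- RR = (10/120)/(1/360) = 30. Fisher exact p = 6.2 × 10⁻⁶. Both agree with the protocol (30; p < 0.0001).
- SE of log RR = √(1/10 − 1/120 + 1/1 − 1/360) = 1.04, so the 95% CI is about 3.9 to 232.

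**2. Could confounding explain that figure?** The most a confounder can inflate a risk ratio is B = RR_EU × RR_UD / (RR_EU + RR_UD − 1), where RR_EU links group to confounder and RR_UD links confounder to outcome.

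| Both risk ratios (assumed) | B | 30/B |
|---|---|---|
| 2 | 1.33 | 22.5 |
| 3 | 1.80 | 16.7 |
| 5 | 2.78 | 10.8 |

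To bring RR 30 down to 1, both would have to reach 30 + √(30 × 29) = 59.5. To bring the lower confidence limit of 3.88 to 1, both would have to reach 3.88 + √(3.88 × 2.88) = 7.2. Parity or ethnicity is not a plausible explanation of a contrast of this size.

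**3. Group sizes.** From section 4.4: 60,000 women a year × 0.80 × 2 years = 96,000; × 0.021 = 2,016 HPA-1a negative; × 0.12 = 242 immunised (the protocol says about 240). That leaves 2,016 × 0.88 = 1,774 HPA-1a negative women without antibodies. At three per negative sample there are 3 × 2,016 = 6,048 HPA-1a positive controls.

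**4. Continuous outcomes.** No adjusted estimate can be computed, because the protocol gives neither the parity or ethnicity distribution by group nor outcome levels by parity or ethnicity. The following only shows how the problem scales. All inputs except the group sizes are assumptions: SD 500, covariate effect 100 (same units), covariate present in 50% of controls and in 60%, 70% or 80% of antibody-positive women, and no true group effect.

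- Bias = 100 × (difference in prevalence) = 10, 20, 30.
- SE = 500 × √(1/240 + 1/1,774) = 34.4; against HPA-1a positive controls, 500 × √(1/240 + 1/6,048) = 32.9.
- Rejection rate = Φ(−1.96 + bias/SE) + Φ(−1.96 − bias/SE).

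| Prevalence in antibody-positive | 240 vs 1,774 | 240 vs 6,048 |
|---|---|---|
| 60% | 6.0% | 6.1% |
| 70% | 9.0% | 9.3% |
| 80% | 14.1% | 14.9% |

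A modest imbalance costs almost nothing; a large one roughly triples the nominal 5% error.

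**5. Can ICH itself be modelled?** Section 4.4 implies 242 × 1/3 × 10% ≈ 8 ICH cases, and the illustrative table has 11 in all. A conventional logistic model with two covariates would be barely supported, so adjustment cannot be the main analysis for ICH.

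**The case against.** The strongest objection is that covariate adjustment of secondary comparisons commonly belongs in a SAP, which is not shown, and that section 10.2 excludes no further analysis. This stands in part: a SAP may already add adjustment. But the protocol is not silent. It names the tests for these comparisons, and all are unadjusted.

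Several stronger readings are tempting, and the objections to them succeed.

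- A reader might infer that parity and ethnicity differ between the groups by design. No section says so or gives a distribution. The ethnicity argument applies only against HPA-1a positive controls; within HPA-1a negative women, HPA-1a type creates no ethnic difference. The parity argument is an inference from how section 1 says antibodies arise.
- A reader might infer from the single control column in the section 10.2 table that the two control groups are pooled. The table is exactly 1:3, the ratio for HPA-1a positive controls. Pooling would give 240 against 1,774 + 6,048 = 7,822, about 1:33. The prose names both groups without saying that they are merged. The column label is at most ambiguous.
- A reader might put a definite size on a bias in birth weight. Any such figure rests wholly on assumed inputs. Birth weight and gestational age at birth are also listed in section 8.1.3 under baseline characteristics, although section 10.2 groups secondary and other parameters together. Hospital stay and morbidity are secondary parameters in section 8.1.2 without any doubt.

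For direct signs of the disease, such as platelet count or petechiae, nothing in the protocol shows that crude tests would mislead.

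**Conclusion.** The point holds in a limited form. Section 10.2 commits to covariate-free tests for a non-randomised comparison with unmatched controls, while the covariates needed for a better analysis are already collected. The risk lies in secondary and other neonatal outcomes that depend on more than FNAIT: hospital days, morbidity, birth weight and gestational age at birth.

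The size is unknown. The 6% to 15% error range depends entirely on the assumed imbalance, covariate effect and SD, and shows only that the effect could be negligible or material.

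It would be wrong to conclude that the main results are at risk. The main study parameter in section 8.1.1 is an incidence, which involves no group contrast, and the illustrative ICH contrast would survive any plausible confounding by these factors. The change is worth making but is not critical.

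**What to change.** In section 10.2, for secondary and other neonatal outcomes with enough events:

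- Make regression adjusted for parity, maternal age and ethnicity the main comparison: linear for continuous outcomes, logistic or log-binomial for binary ones. State in advance how many events are enough.
- Do not adjust for gestational age at birth or mode of delivery, which may be effects of the disease.
- Report two separate contrasts, each with a 95% CI: antibody-positive against HPA-1a negative antibody-negative women, and antibody-positive against HPA-1a positive women. State which group the control column of the table represents.
- Keep the chi-square, Fisher, t and Mann-Whitney tests as supportive analyses.
- For very sparse outcomes such as ICH, keep Fisher's exact test as the main test, with a penalised (Firth) model as a sensitivity analysis if wanted.

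The cost is a little more analysis work and slightly wider intervals. No new data are needed.

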### 10.3 Interim analysis

*Not applicable*

## **11 ETHICAL CONSIDERATIONS**

### **11.1 Regulation statement**

The design of this study, not involving any additional or invasive tests, ensures that it is not subject to the Medical Research Involving Human Subjects Act (In Dutch: Wet Medisch Wetenschappelijk onderzoek met Mensen; WMO). Therefore, the legal framework of our study is laid out in the Medical Treatment Agreement Act (in Dutch: Wet Geneeskundige Behandelingsovereenkomst). The study will be conducted in accordance with this Medical Treatment Agreement Act, expanded in the Codes for Good Behaviour and Good Use (in Dutch: Code Goed Gebruik en Code Goed Gedrag), developed by the Federation of Medical research Committee (In Dutch: Federatie van Medisch Wetenschappelijke Verenigingen (FMWV)).

### **11.2 Recruitment and consent**

As stated above the legal framework for our specific study design is presented in the Medical Treatment Agreement Act. This act states that passive consent can only be applied in case of completely not retraceable material. Because we need to contact obstetric caregivers to obtain clinical information after performing tests, this procedure does not apply to our study design. We will therefore be obtaining active informed consent, using the same application form that is already been used for consenting to an requesting for the regular RhD and Rhc screening performed by Sanquin. Because our research is not subject to the WMO, we will not be obtaining a separate signed consent form.

To make sure all pregnant women are adequately informed about the study, and can therefore be making a well informed choice, RhD negative and Rhc negative pregnant women in the Netherlands will be receiving an information flyer, provided by their obstetric care givers. On the application form for the regular RhD and Rhc screening at 27th weeks gestation, there will be two additional boxes, one for declining to participate in our study and one for consenting to participate in our study.

RhDRhc

### **11.3 Objection by minors or incapacitated subjects**

RhD negative and Rhc negative pregnant women will be informed by their obstetric care givers about the HIP study as well as being asked to participate. Obstetric care givers will be making sure that pregnant women that are underage or evidently unable to understand what it means to participate in our study will be excluded. All obstetric care givers will be informed about this procedure before starting the study.

### **11.4 Benefits and risks assessment, group relatedness**

Screening programs require a careful balance between benefit and potential harm. Women receiving the message that they are among the 2% HPA-1a negative women, and therefore at risk for bleeding in their child, obviously will worry about adverse outcome until they are reassured by other testing, or ultimately by the birth of a healthy child. Therefore nor the participating pregnant women, nor the obstetric caregiver will be informed about the serological HPA-1a typing results. Also, we decided to perform the antibody detection test after birth. Thus no additional information can be known that would otherwise change the management of the current pregnancy, according to the Dutch Guidelines. Consequently, there will be no direct benefit for the pregnant women during this pregnancy.

### **11.5 Compensation for injury**

*Not applicable*

## **12 ADMINISTRATIVE ASPECTS, MONITORING AND PUBLICATION**

### 12.1 Handling and storage of data and documents

Data of participants will be handled confidentially. When samples of participants are being tested these have already been given a unique (bar)code, which is not directly retraceable to the patient. Once included in the study (the HPA-1a negative women as well as the HPA-1a positive controls) the unique (bar)code will be linked to an unique study-code. The results of the serological HPA-1a typing, as well as the HPA-1a alloantibody screening, will be linked to this unique study-code. The key to these codes (from barcode to study-code) will be safeguarded by the head of the laboratory for red blood cell diagnostics ([name], PhD). For collecting the clinical data concerning the pregnancy, delivery and first postnatal period as well as the baseline characteristics, the analysts will supply the researcher with a list of included patients (barcodes) and their obstetric care givers without disclosing the results of HPA-1a typing or antibody screening. This process is also described in chapter 8.2 and 8.3. All personal data will be handled according to the Dutch Personal Data Protection Act (in Dutch: De Wet Bescherming Persoonsgegevens, Wbp).

### 12.2 Monitoring and Quality Assurance

*Not applicable*

### 12.3 Amendments

Amendments are changes made to the research after a favourable opinion by the accredited METC has been given. All substantial amendments will be notified to the METC that gave a favourable opinion. Non-substantial amendments will not be notified to the accredited METC and the competent authority, but will be recorded and filed by the sponsor.

### 12.4 Annual progress report

We will be submitting a summary of the progress of the trial to the accredited METC once a year. Information will be provided on the date of inclusion of the first subject, numbers of subjects included and numbers of subjects that have completed the trial, serious adverse events/ serious adverse reactions, other problems, and amendments.

### 12.5 End of study report

We will be notifying the accredited METC of the end of the study within a period of 8 weeks. The end of the study is defined as the last patient's delivery. In case the study is ended prematurely, the investigator will notify the accredited METC within 15 days, including the reasons for the premature termination. Within one year after the end of the study, we will be submitting a final study report with the results of the study, including any publications/abstracts of the study, to the accredited METC.

### 12.6 Public disclosure and publication policy

There is no prearranged policy with the sponsor about publication. However in general we prefer to publish in an open access journal.

## **13 STRUCTURED RISK ANALYSIS**

*Not applicable*

